6.3 Breast Cancer Genetic Testing

Study participants with a family history suggestive of a pathogenic variant and/or with an elevated BC risk who meet NCCN genetic testing guidelines ([Appendix 2](#))^{1, 2} will be referred to the Cancer Genetics Clinic to undergo a formal genetic counseling session and possible germline genetic testing. Genetic testing will be performed via the Ambry Genetics® Panel, which is our current institution standard.

Persons who undergo genetic testing and are found to have a pathogenic variant for BC will be offered to see the PI, [name], to discuss the utility of risk-reducing mastectomies as part of their chest masculinization operation (see Visit 2). Persons who are found to have a pathogenic variant that infers any other risk besides BC will be referred to the appropriate care teams for further evaluation, as is the current standard practice in our Genetics clinic.

6.4 Visit 2: Surgical Risk-Reducing Mastectomy Counseling

Participants considering risk-reducing mastectomies will meet directly with [name] who can perform the operation in tandem with the patient's respective plastic surgeon. Patients who decline risk-reducing mastectomy as part of their surgery will be given the opportunity to express why they declined. This procedure is consistent with the current clinical workflow for cisgender patients. If patients undergo risk-reducing mastectomy as part of their chest masculinization surgery, pathological tissue examination is standard and findings will be collected during the study period.

6.5 Data Factors

Data factors to be collected from study participants for analysis described in [Section 9.2.2](#) include the following:

- Name
- DOB
- MRN
- Age
- Weight (lbs)
- Height (inches)
- BMI
- Race
- Ethnicity
- Highest Level of Education
- Insured?
 - If so, type
- Sex Assigned at Birth
- Gender Identity
- Gender Expression
- Sexual Identity
- History of Gender Affirming Hormone Therapy
 - Duration
 - Dosage
 - Laboratory Values (estrogen, progesterone, and testosterone history)
- Prior Gender-Affirming Surgeries
- Age at First Menstrual Period
- Age at First Live Birth
 - Number of Children
- Family History Status Known or Unknown?
 - Unknown – Maternal, Paternal, or Both Sides?
- Number of 1st Degree Relatives with BC
- Number of 2nd Degree Relatives with BC
- Number of 1st Degree Relatives with Ovarian Cancer
- Number of 2nd Degree Relatives with Ovarian Cancer
- Any Other 1st or 2nd Degree Relatives with Any Cancer Diagnosis and What Type
- Previous Breast Biopsy

- If Yes, Atypical Cells
 - If Yes, Pathology
- Any History of Hormone Replacement Therapy (Not Including Gender-affirming Testosterone Therapy)
- Any Ashkenazi Jewish Inheritance?
- Date of Risk Estimation
- Participant's Personal Estimation of Lifetime Risk
- Gail Model Risk Estimate
- IBIS Model Risk Estimate
- Average Risk ([Gail + IBIS Risks]/2)
- Recommended to Undergo Risk-reducing Mastectomies as Part of Top Surgery (Risk 17-30%) (Y/N)
- Given the Option to Consider Risk-reducing Mastectomies as Part of Top Surgery (Risk 17-30%) (Y/N)
- Say they would choose to Undergo Top Surgery (Y/N)
- Underwent Top Surgery (Y/N)
- Underwent Risk-reducing Mastectomies as Part of Top Surgery (Y/N)
- Recommended to Undergo Genetic Counseling (Y/N)
- Underwent Genetic Counseling (Y/N)
- Recommend to Undergo Genetic Testing (Y/N)
- Underwent Genetic Testing (Y/N)
 - If yes, results:

7.0 SUBJECT WITHDRAWAL, END OF STUDY, AND STUDY DISCONTINUATION

7.1 Subject Withdrawal

7.1.1 Patient-Initiated Withdrawal

A participant may decide to withdraw from the study at any time.

7.1.2 Investigator-Initiated Withdrawal

The investigator may withdraw a participant whenever continued participation is no longer in their best interests. Reasons for withdrawing a participant include, but are not limited to, a subject's request to end participation, a subject's noncompliance, or simply significant uncertainty on the part of the investigator that continued participation is prudent.

7.1.3 Replacement Policy and Data Usage

Subjects who sign the informed consent form and are enrolled, but subsequently withdraw, will be replaced. Data collected from subjects that withdraw or discontinue from the study will not be used.

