Visual Analog Scale		X			
Personalized BC Risk Assessment (Gail and/or IBIS model)		X			
Genetic Counseling ^b			X ^b		
Genetic Testing ^b			X ^b		
Surgical Oncologist Risk-Reducing Mastectomy Counseling Session ^c				X ^c	
Data Collection		X	X	X	X
Adverse Events Collection		X	X	X	

Footnotes

- ^a During Visit 1, the study team will be available to answer any additional questions the potential participant may have about the study and confirm whether they were consented. If not done so already and as an option, a potential participant will have the opportunity to sign the informed consent form in person.
- ^b Only those study participants with a family history suggestive of a pathogenic variant and/or with an elevated breast cancer risk who meet genetic testing guidelines ([Appendix 2](#))^{1, 2} will be referred to the Cancer Genetics Clinic to undergo a formal genetic counseling session and possible germline genetic testing. Genetic testing will be performed via the Ambry Genetics® Panel per institutional standards. See [Section 6.3](#) for additional details.
- ^c Only those study participants with an estimated lifetime breast cancer risk >17% (defined by the Gail model [<https://ibis.ikonopedia.com>]) and/or IBIS model [<https://www.mdcalc.com/calc/3647/gail-model-breast-cancer-risk>]) or with a pathogenic germline mutation known to increase breast cancer risk will be offered to meet with the PI to discuss the utility of considering risk-reducing mastectomies as part of their chest masculinization surgery. If a subject is referred to the Cancer Genetics Clinic, Visit 2 is to occur after their Cancer Genetics Clinic visit.
- ^d Participants with an estimated lifetime breast cancer risk >17% may be followed-up once within 60 days after the end of the funding period to determine if they either (i) underwent their chest masculinization surgery with or without the risk-reducing mastectomies, (ii) scheduled but did not undergo their chest masculinization surgery with or without the risk-reducing mastectomies, or (iii) say they would choose to schedule/undergo risk-reducing mastectomies as part of their chest masculinization surgery. Regarding (i) and (ii), follow-up data will only be collected from participants that had their procedure(s) performed by a MCW Plastic Surgery team member (study Co-Is) and, in certain instances, the study PI.

LIST OF ABBREVIATIONS

AE	adverse event
BC	breast cancer
CDH1	cadherin 1
CFR	Code of Federal Regulations

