7.2 End of Study Definition

A subject is considered to have completed the study if they have completed all phases of the study including the last scheduled procedure shown in the [Study Calendar](#) or has been discontinued.

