9.2 Analysis Plan

9.2.1 Analysis Population

Data from all participants will be used for endpoint analyses. Data from subjects who withdraw or discontinue will be not used.

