9.3 Missing Data

No major missing data relevant to the primary endpoints are anticipated. Unforeseen missing data, if any, will be addressed in consultation with the study statistician.

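### Sections 7.1.3 and 9.2.1 discard completed Visit 1 results when a participant later withdraws or discontinues; if elevated-risk participants leave more often, expected prevalence is biased down

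*Combined protocol and SAP*

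**What the plan says.** Section 7.1.3 (Replacement Policy and Data Usage) contains two rules. On replacement: "Subjects who sign the informed consent form and are enrolled, but subsequently withdraw, will be replaced". On data: "Data collected from subjects that withdraw or discontinue from the study will not be used". Section 9.2.1 (Analysis Population) opens with "Data from all participants will be used for endpoint analyses" and then adds "Data from subjects who withdraw or discontinue will be not used". Neither section distinguishes data obtained before departure from data that would have come later.

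Other parts of the protocol bear on how the rule works:

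- Sections 7.1.1 and 7.1.2 allow the participant to withdraw at any time. They also let the investigator withdraw someone, for reasons that include noncompliance.
- Section 6.2 places the Visual Analog Scale (VAS) and the Gail/IBIS calculation at Visit 1. Average-risk participants have no second visit.
- Study Calendar footnote c ties Visit 2 to lifetime risk above 17% or a pathogenic variant. Footnote d adds: "Participants with an estimated lifetime breast cancer risk >17% may be followed-up once within 60 days after the end of the funding period".
- Section 7.2 says "A subject is considered to have completed the study if they have completed all phases of the study", and extends that status to a subject who meets the alternative condition "or has been discontinued".
- Section 9.3 says "No major missing data relevant to the primary endpoints are anticipated" and refers any unforeseen missing data to the study statistician.

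**The concern.** By the end of Visit 1, two quantities are fixed for each participant: self-perceived risk and calculated risk. Under Section 2.2 they determine the risk-prevalence part of endpoint 1 and the whole of endpoint 3, and no later event changes them. Deleting them because someone leaves afterwards has no analytic benefit.

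It can also do harm, because departure may be related to the result. Participants hear their risk at Visit 1, and Sections 8.0 and 11.5.1 foresee possible distress on hearing it. After that, those with elevated risk have more study contact, and so more occasions to withdraw or be discontinued. If they leave more often, the analysed sample under-represents exactly the group whose frequency is being estimated. Replacement does not help, since replacements pass through the same filter.

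The route is true withdrawal or investigator discontinuation. Declining genetics, Visit 2 or mastectomy is treated as a recorded choice (Sections 6.1, 6.2, 6.4 and 6.5) and should leave the person in the analysis.

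Endpoint 2 is exposed in a different way: its denominator is expected to be so small that one exclusion can move it substantially in either direction. Because the plan does not require withdrawals to be reported by risk category, a reader could not tell which situation had arisen.

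**Working it through.** **Inputs from the documents (Section 9.1).** N = 35; 4 participants assumed to have elevated risk; 90% exact confidence interval; stated margin of error 10%.

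**Inputs that are assumptions.** Withdrawal rates after Visit 1, w1 for elevated-risk and w0 for average-risk participants, and an uptake of 2 out of 4 for endpoint 2. The documents give none of these, so a range is shown for the rates.

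**Step 1: the plan's own figure.** p = 4/35 = 11.4%. The Clopper-Pearson 90% limits are the 5th percentile of Beta(4, 32) and the 95th percentile of Beta(5, 31), that is 4.0% and 24.3%. Half the width is 10.1 points, so the stated 10% is reproduced.

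**Step 2: expected prevalence under the rule.** With exclusion and replacement until 35 are retained, the expected proportion is

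p(1 − w1) / [p(1 − w1) + (1 − p)(1 − w0)].

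For w1 = 20% and w0 = 5%: 0.1143 × 0.80 = 0.0914; 0.8857 × 0.95 = 0.8414; 0.0914 / (0.0914 + 0.8414) = 9.8%.

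| w1 (elevated) | w0 (average) | Expected prevalence | Shift from 11.4% |
|---|---|---|---|
| 5% | 5% | 11.4% | none |
| 10% | 5% | 10.9% | −0.5 points |
| 20% | 5% | 9.8% | −1.6 points |
| 30% | 5% | 8.7% | −2.7 points |
| 0% | 5% | 12.0% | +0.5 points |

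A simulation of replacement until 35 are retained gave 8.6% for 30%/5% and 11.4% for 20%/20%, in agreement with the formula. If all completed Visit 1 results were kept, the expectation would be 11.4% in every row.

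**Step 3: how likely a loss is.** The chance that at least one of 4 elevated-risk participants is lost is 1 − (1 − w1)^4: 18.5% at a 5% rate, 34% at 10% and 59% at 20%. Expected losses are 4 × w1 = 0.2, 0.4 and 0.8 people.

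**Step 4: effect of a single loss.** Suppose one elevated-risk participant is lost and replaced at random. The result is 3/35 = 8.6% if the replacement is average risk (probability 31/35 = 88.6%) and 4/35 = 11.4% if elevated risk (probability 4/35 = 11.4%). The mean is (3 + 4/35)/35 = 8.9%.

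**Step 5: direction in individual samples.** Start from 4 elevated and 31 average. Take losses as Bin(4, w1) and Bin(31, w0), with replacements drawn at the Step 2 prevalence. Exact enumeration gives the analysed elevated-risk count:

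| w1 / w0 | Below 4 | Equal to 4 | Above 4 |
|---|---|---|---|
| 5% / 5% | 14% | 72% | 14% |
| 10% / 5% | 27% | 62% | 11% |
| 20% / 5% | 49% | 44% | 7% |

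The downward direction is therefore a statement about the expectation, not about every sample.

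**Step 6: endpoint 2.** If 2 of 4 would choose mastectomy (50%), losing one decliner gives 2/3 = 67% and losing one acceptor gives 1/3 = 33%.

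**Step 7: consistency of the wording.** Section 7.2 gives a discontinued subject the status of having completed the study, while Sections 7.1.3 and 9.2.1 discard that subject's data. Section 7.1.3 provides replacement only for those who withdraw, so it is unclear whether a discontinued subject is replaced.

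**The case against.** The strongest reply is that the rule may rarely apply. No withdrawal rate is given, and nothing shows that elevated-risk participants leave more often. The Protocol Summary describes an assessment of about 30 minutes followed by record review, Section 6.1 treats later activities as participant choice and standard practice, and footnote d's follow-up is optional and happens once. There is little to withdraw from. The contrast in contact is also softer than the Visit 2 rule suggests: Sections 6.2 and 6.3 also lead to genetics contact on family-history grounds, so some participants at or below 17% have later contact too. Many withdrawals could fall between consent and Visit 1, where replacement is sensible. In a descriptive pilot, shifts of 0.5 to 2.7 points against a half-width of 10.1 points are small. Finally, the consent pages are not in the reviewed copy and may promise that withdrawn participants' data will not be used.

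Most of this stands as a limit on size. It does not justify the rule. Few losses are no reason to delete valid primary data, and the confidence interval describes sampling error, not selection on the outcome. That selection would not shrink in the 125-person study that Section 9.1 anticipates with a 5% margin. Section 9.3's referral to the statistician covers unforeseen missing data, whereas this is a planned exclusion. The consent point is real and is built into the fix. On Section 7.2, it is fair to say that a definition of when participation ends is not a data-use rule, so that item is a request for clarification only.

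**Conclusion.** The concern holds and should be fixed. The exclusion is explicit in two sections, makes no exception for a completed Visit 1, and can depend on the result being estimated. If elevated-risk participants withdraw more often, expected prevalence is biased down; at equal rates there is no bias, and if the difference reverses the bias is upward. The size depends wholly on assumed withdrawal rates, and every shift tabulated above lies well inside the plan's exact 90% interval. Confidence is high that the rule exists and that the conditional direction is right. How often it will operate is unknown. The endpoint 2 figures also rest on an assumed uptake and on a denominator of about 4, taken from Section 9.1's elevated-risk count; any variant carriers at or below 17% would add to it.

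**What to change.** Amend Sections 7.1.3 and 9.2.1 as follows.

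1. For endpoint 1's risk prevalence and for endpoint 3, analyse everyone with a completed Visit 1 VAS and risk assessment. Use data collected up to withdrawal, where consent allows and unless the participant asks for removal.
2. Replace only those who leave before the Visit 1 assessment.
3. Subject to the same consent limit, keep identified elevated-risk or variant-positive participants in the endpoint 2 denominator, and show those with no stated choice as a separate category.
4. Report the number of withdrawals by risk category.

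As clarification, state that declining genetics, Visit 2 or mastectomy is neither withdrawal nor noncompliance. Also reconcile Section 7.2's treatment of discontinued subjects with Sections 7.1.3 and 9.2.1, including whether they are replaced.

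The cost is a wording amendment, a check of the consent language on data kept after withdrawal, and slightly more reporting. No additional patients are needed, and there would be fewer replacements.

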7.2 End of Study Definition

A subject is considered to have completed the study if they have completed all phases of the study including the last scheduled procedure shown in the [Study Calendar](#) or has been discontinued.

7.3 Study Discontinuation and Closure

This study may be temporarily suspended or prematurely terminated if there is sufficient reasonable cause (as determined by the MCW study principal investigator, DSMC, sponsor, and/or IRB). Written notification, documenting the reason for study suspension or termination, will be provided by the suspending or terminating party to study participants, investigator, funding agency, and regulatory authorities. If the study is prematurely terminated or suspended, the MCW principal investigator (PI) will promptly inform the MCW Institutional Review Board (IRB) and sponsor and will provide the reason(s) for the termination or suspension. Study participants will be contacted, as applicable, and be informed of changes.

8.0 ADVERSE EVENTS: DEFINITIONS, COLLECTION, AND REPORTING

This study is considered to be of minimal risk to participants due to its design and the nature of the intervention being tested (*i.e.*, risk assessment, genetic testing, and patient education). As described in [Section 11.5.1](#), participants may experience anxiety or distress upon hearing the results of their personalized BC risk assessment and/or their genetic tests.

Subjects will not undergo an investigational medical intervention for the purposes of this study. While the participants' decision to have risk-reducing mastectomies performed in tandem with their gender-affirming chest masculinization procedure will be assessed, the risk-reducing mastectomy procedure itself or its outcomes does not fall under this study protocol. For these reasons, adverse and serious adverse events are not expected, but will be defined, collected, and reported as described in this section if encountered.

8.1 Definitions

8.1.1 Adverse Event (AE)

Any untoward medical occurrence in a subject or clinical investigation subject administered an interventional product and which does not necessarily have to have a causal relationship with this treatment.

This study will utilize the NCI Common Terminology Criteria for Adverse Events (CTCAE) version 5.0, located on the CTEP web site:

https://ctep.cancer.gov/protocolDevelopment/electronic_applications/ctc.htm

AEs may be spontaneously reported by the subject and/or in response to an open question from study personnel or revealed by observation, physical examination or other diagnostic procedures.

8.1.2 Serious Adverse Event (SAE)

Serious Adverse Event (SAE) means any untoward medical occurrence that results in any of the following outcomes:

- **Death.** Results in death.
- **Life-threatening.** Is life-threatening (refers to an AE in which the participant was at risk of death at the time of the event. It does not refer to an event which hypothetically might have caused death if it were more severe).
- **Hospitalization.** Requires inpatient hospitalization ≥ 24 hours or prolongation of an existing hospitalization.
- **Disability/incapacity.** Results in persistent or significant disability or incapacity. (Disability is defined as a substantial disruption of a person's ability to conduct normal life functions).
- **Pregnancy**
- **Medically important event.** This refers to an AE that may not result in death, be immediately life threatening, or require hospitalization, but may be considered serious when, based on appropriate medical judgment, may jeopardize the participant, require medical or surgical intervention to prevent one of the outcomes listed above, or involves suspected transmission via a medicinal product of an infectious agent. Examples of such medical events include allergic bronchospasm requiring intensive treatment in an emergency room or at home, blood dyscrasias or convulsions that do not result in inpatient hospitalization, or the development of drug dependency or drug abuse; any organism, virus, or infectious particle (e.g., prion protein transmitting transmissible spongiform encephalopathy, pathogenic or nonpathogenic, is considered an infectious agent).

8.1.3 Attribution of an Adverse Event

An assessment of the relationship between the adverse event and the medical intervention, using the following categories:

- **Definitely Related:** *The AE is clearly related to the intervention.* There is clear evidence to suggest a causal relationship, and other possible contributing factors can be ruled out.
- **Probably Related:** *The AE is likely related to the intervention.* There is evidence to suggest a causal relationship, and the influence of other factors is unlikely.
- **Possibly Related:** *The AE may be related to the intervention.* There is some evidence to suggest a causal relationship (e.g., the event occurred within a reasonable time after administration of the trial medication). However, the influence of other factors may have contributed to the event (e.g., the subject's clinical condition, other concomitant events).
- **Unlikely:** *The AE is doubtfully related to the intervention.* A clinical event, including an abnormal laboratory test result, whose temporal relationship to drug administration makes a causal relationship improbable (e.g., the event did not occur within a reasonable time after administration of the trial medication) and in which other drugs or chemicals or underlying disease provides plausible explanations (e.g., the subject's clinical condition, other concomitant treatments).

- **Unrelated:** *The AE is clearly NOT related to the intervention.* The AE is completely independent of study drug administration, and/or evidence exists that the event is definitely related to another etiology.

8.1.4 Expectedness of an Adverse Event

Study Investigator or treating physician will be responsible for determining whether an AE is expected or unexpected as indicated in the protocol, informed consent form and/or drug information brochure. An AE will be considered unexpected if the nature, severity, or frequency of the event is NOT consistent with the risk information previously described for the study intervention.

8.2 Collection and Reporting Requirements for Adverse Events and Serious Adverse Events

Adverse and serious adverse events are not expected, but if such events occur, they will be reported per IRB guidelines. Any events reported to the IRB will be reported to the DSMC following the same manner (routine or expedited).

For routine reporting, the events will be reported to the IRB as part of the annual continuing progress report, and the DSMC will review events entered into OnCore™ at the time of scheduled monitoring.

For expedited DSMC reporting, the study coordinator/research nurse must notify the DSMC via email. For AEs, include the subject ID, date of event, grade, relatedness, expectedness, and a short narrative. For SAEs, DSMC will review the SAE report entered into the secure Microsoft Excel spreadsheet used for the study.

